Aim 1: successive rounds of virtual focus groups conducted over Zoom to adapt the EMPOWER educational tool for people living with dementia (PLWD) receiving CNS polyRx and their care partners (CPs). Brief follow-up phone calls with select care partners who participated in the focus group discussion in order to reflect on and clarify any feedback and insight that emerged during the group discussion.

Aims 2 and 3: use the electronic health record (EHR) to identify a list of PLWD experiencing CNS polyRx and (b) a randomized-controlled clinical trial implementing the adapted EMPOWER intervention in two primary care clinics using pragmatic methods at University of Michigan Health and Henry Ford Health (n=120 PLWD). We will also interview prescribing clinicians to obtain their perspectives on barriers and facilitators to the intervention.

Interventions and Duration

Participants (i.e., PLWD experiencing CNS polyRx) will be mailed the educational tool. Four months after sending the tool, we will do a final EHR query for all participants to assess the burden of CNS polyRx (i.e., total standardized daily dosage) and determine whether the prescribing regimen changed from the medications prescribed at baseline. Participation will be over after the 4 months.

Sample Size and Population

Our goal is to include 4 participating clinics with at least 30 PLWDs with active CNS polyRx per clinic, for a total of about 120 eligible PLWDs.

STUDY TEAM ROSTER

Principal Investigator:

[name], MS

[name]

[name]

[contact]

[contact]

Main responsibilities/Key roles:

As the Principal Investigator, [name] will take primary responsibility for overall scientific direction and oversight of the project. [name] will: 1) lead the development of the educational tool for Aim 1; 2) work with Drs. [name] and [name] to oversee quantitative data collection and analysis for all aims, supported by data analyst; 3) work with [name] to oversee focus group and qualitative interviews and analysis, supported by study qualitative coordinator; 4) along with Co- Investigators, prepare research reports and manuscripts for peer-reviewed publication; 5) provide overall supervision of study staff.

Co-Investigators:

[name]

[name]

[name]

[contact]

[contact]

Main responsibilities/Key roles:

1 STUDY OBJECTIVES

1.1 Primary Objective

The primary clinical outcome will be change in the total standardized daily dosage (TSDD) of the medication classes contributing to CNS polyRx as measured in the EHR, from baseline to 4 months after sending the adapted intervention. We hypothesize that the TSDD of the medication classes contributing to CNS polyRx will decline from baseline to 4 months in participants receiving the nudge intervention (though this pilot study is not designed [or powered] to detect a statistically significant change).

1.2 Secondary Objectives

- Adapt an educational nudge intervention to help motivate CNS polyRx deprescribing among PLWD
- Establish mailing of the educational brochure within the clinic workflow by engaging clinicians and pharmacists at each of the identified clinics
- Establish implementation feasibility: after sending the tool, the proportion of enrollees with documentation in the EHR of discussion regarding CNS-active medications with a prescribing clinician (or pharmacist).

2 BACKGROUND AND RATIONALE

2.1 Background on Condition, Disease, or Other Primary Study Focus

The number of people living with Alzheimer’s disease or a related dementia (PLWD) in the U.S. is projected to grow to 50 million people by 2050. Although cognitive impairment is the clinical hallmark of dementia, behavioral and psychological symptoms of dementia (BPSD) such as apathy, delusions, agitation, and sleep disturbances are exceedingly common, occur in all forms of dementia, and often dominate disease presentation.¹⁻⁵ Nearly all patients will exhibit these symptoms at some point in the course of dementia.^{3,6} Such symptoms, as opposed to core cognitive symptoms, are particularly vexing and create the most difficulties for patients, caregivers, and clinicians, leading to earlier nursing home placement.⁷⁻¹³ Central nervous system-active medications are widely prescribed to PLWD in the community to address these symptoms. In a recent *JAMA* publication by [name] team analyzing all traditional Medicare beneficiaries living with dementia who had Part D prescription drug coverage, 73.5% filled a prescription for at least one CNS medication, despite the minimal evidence of efficacy among PLWD while 13.9% of community-dwelling PLWD were exposed to CNS polyRx, defined as >30 days of concurrent exposure to ≥3 CNS medications.¹⁴ CNS medication use—singly and in combination—poses specific risks for older adults overall and PLWD specifically given the adverse impact on cognition and potential for harms including fall-related injury and death.

2.2 Study Rationale

The health care system is poorly equipped to deal with the growing number of persons living with dementia (PLWD) and their complex medical and psychosocial needs, which may help explain their high rate of potentially inappropriate psychotropic and opioid polypharmacy. However, there is potential for direct-to-patient education to promote deprescribing. The power of a direct-to-patient educational nudge approach has been highlighted by the EMPOWER intervention, which specifically focused on and successfully achieved sedative-hypnotic (e.g.,

benzodiazepines) deprescribing in older adults. Critically for this proposal, a *post hoc* analysis found no difference in efficacy between participants with and without mild cognitive impairment. Based on the potential demonstrated by EMPOWER, a direct-to-patient approach may be a helpful mechanism to prompt CNS polyRx deprescribing among PLWD. Therefore, we will adapt direct-to-PLWD educational nudge to address such polypharmacy. This educational intervention poses minimal risks to participants, particular given that the “usual care” being targeted (CNS polyRx) in fact poses significant risks to PLWD.

3 STUDY DESIGN

- *Type/design of trial (e.g., placebo-controlled, double-mask, parallel design, open-label, dose escalation, dose-ranging)*

This is an educational nudge intervention with two intervention clinics and two control clinics.

- *Specific statement of the primary and secondary outcomes (must be consistent with Study Objectives)*

The primary clinical outcome will be change in the total standardized daily dosage (TSDD) of the medication classes contributing to CNS polyRx as measured in the EHR, from baseline to 4 months after sending the adapted intervention. We hypothesize that the TSDD of the medication classes contributing to CNS polyRx will decline from baseline to 4 months in participants receiving the nudge intervention (though this pilot study is not designed [or powered] to detect a statistically significant change).

Secondary Objectives are:

- a. Adapt a patient- oriented educational nudge intervention to help motivate CNS polyRx deprescribing among PLWD
- b. Establish mailing of the educational brochure within the clinic workflow by engaging clinicians and/or pharmacists at each of the participating clinics
- c. Establish implementation feasibility: after sending the tool, the proportion of enrollees with documentation in the EHR of discussion regarding CNS-active medications with a prescribing clinician (or pharmacist).

- *Study population and groups/arms including sample size (including a table, if appropriate)*

We will identify 120 PLWD experiencing CNS polyRx across participating clinics to receive the intervention.

- *Study location (e.g., in-patient or out-patient, clinic, community)*

A total of four primary care clinics at University of Michigan Health and Henry Ford Health; potentially more clinics will be engaged if necessary to reach the goal of N=120 PLWD.

- *Approximate duration of enrollment period and follow-up (specify individual participant vs. entire trial)*

Approximately 6 months accounting for EHR review, sending the nudge tool, and then allowing several months (4) afterwards for dyads to discuss with clinicians and make medication changes.

- *Description of intervention and administration*

An adapted EMPOWER brochure that will specifically be modified to address CNS polyRx (as opposed to the single-class focus of the original). The intervention will be adapted based

on input from successive rounds of focus groups and then administered by mail through the clinic. There is no direct interaction between the study team and PLWD

- *Randomization, blinding and any stratification*

There is no patient-level randomization. Within each health system (University of Michigan and Henry Ford), we will randomly select one of the clinics where patients will receive the nudge intervention.

- *Other protocol specific details, such as centralization of evaluations (e.g., central laboratory or central reading center for clinical scans).*

n/a

4 SELECTION AND ENROLLMENT OF PARTICIPANTS

4.1 Inclusion Criteria

Aim 1: Focus Group Research

The inclusion criteria for the Person living with Dementia (PLWD) will be:

- (1) Individuals with a self-reported diagnosis of dementia of any type and experiencing no more than mild dementia;
- (2) Individuals that are able to read, speak and understand English;
- (3) Individuals that have a care partner (CP)
- (4) Individuals that are 50 years of age or older.

The inclusion criteria for the care partner (CP) will be:

- (1) Individuals who are 18 years of age or older or considered legal adults in their state of residence;
- (2) who are able to read, speak and understand English;
- (3) Individuals who are identified as the CP to the PLWD.

Aim 2 and 3: Intervention

The inclusion criteria for the Person living with Dementia (PLWD) will be:

- (1) Individuals who are receiving care at the one of the selected primary care clinics at Michigan Medicine and Henry Ford Health System;
- (2) Individuals who have a diagnosis of dementia or mild cognitive impairment (MCI) of any type based on ICD-10 codes;
- (3) Individuals who have been prescribed ≥ 3 of the medications that contribute to CNS polyRx (e.g., antidepressants, antipsychotics, anti-epileptics, benzodiazepines, non-benzodiazepine benzodiazepine receptor agonist hypnotics, or opioids) based on chart review;
- (4) Individuals that are 50 years of age or older.

4.2 Exclusion Criteria

Aim 1: Focus Group Research

The exclusion criteria for PLWD will be:

- (1) Individuals who do not read, speak, or understand English;
- (2) Individuals with a diagnosis of dementia that is in severe stage;
- (3) Individuals with visual impairment that would prohibit viewing study materials;

(4) Individuals with hearing impairment sufficient to prohibit participation in a focus group.

The exclusion criteria for CPs will be:

- (1) Individuals who do not read, speak or understand English;
- (2) Individuals with any visual impairment that would prohibit viewing study materials;
- (3) Individuals with any hearing impairment that would prohibit participation in a focus group.

Aim 2 and 3: Intervention

(4) After identifying potential participants through EHR at the intervention and control clinics, we will provide the list to their primary care clinicians to review and opt-out potential participants for whom they feel the intervention is not appropriate. (While the control clinics will *not* receive the intervention, we will still allow their clinicians to indicate PLWD for whom they think the intervention would be inappropriate in order to have the most comparable groups.) At intervention sites, clinicians will also be given the opportunity to suggest any additional patients at the clinic who meet the inclusion criteria and may have been missed by the EHR search. The opt out letter and responses will be sent by email to/from the research assistant or coordinator at each respective site and the clinic liaison. If doctors wish to suggest any additional patients, those patients will be added to REDCap by the health system's own research team. Patients selected in this way will be noted in REDCap as having been selected through this alternate method.

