Identifying and recruiting trial participants: Patients in Aim 2 and 3 will not be recruited directly to participate.

Eligibility and Ineligibility criteria: We will use the electronic health record (EHR) to identify patients living with dementia prescribed these problematic medication combinations (2a). Team data analysts will use DataDirect—the portal for researchers into the Michigan Medicine and HFHS EHRs—to identify PLWD seen in primary care with CNS-active polyRx. ICD-10 codes will be used to identify PLWD (including MCI) with an ambulatory care encounter with a primary care clinician (internal medicine, family medicine, or geriatrics) during the preceding 12 months. Within each system, we will identify a pair of clinics that have relatively similar panel characteristics (similar volume overall; PLWD with similar distributions of gender, race/ethnicity) to serve as the paired intervention-control sites. Among PLWD, we will use current outpatient medications data to identify those with ≥ 3 active prescriptions of the medications that contribute to CNS polyRx (e.g., antidepressants, antipsychotics, anti-epileptics, benzodiazepines, non-benzodiazepine benzodiazepine receptor agonist hypnotics, or opioids). We will contact the primary care clinicians of eligible PLWD once by email to offer them the opportunity to exclude potential PLWD participants for whom they think the intervention would be inappropriate; clinicians will have one week to opt potential participants out, or to suggest an eligible patient we may have missed (if they do not reply, we will assume that we can proceed).

Randomization: We will randomly select one clinic (or more, as needed to meet the target dyad sample size) within each system as the intervention clinic; dyads in these clinics will receive the nudge intervention. Dyads within the other clinic in each system will serve as controls.

Consent procedures: We will request a waiver of informed consent for PLWD participants in Aim 2 and 3. See section 11.2 for details.

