6 STUDY PROCEDURES

6.1 Schedule of Evaluations

Assessment	Month 1-2	Month 3-4	Month 5-6	Month 7-8	Month 9-10	Month 11-12
Draft adapted tool	x					
Adapt content (focus groups x3)		x	x			
Follow-up phone calls		x	x			
Screen/Identify target PLWD in EHR			x			
Allow clinician opt-out of participants			x			
Clinic randomization			x			
Mailing of educational tool				x		
2-month chart review				x		
4-month chart review					x	
Clinician Interviews						x
Adverse Events				x	x	x

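### Section 4.2 offers patient addition at intervention sites and section 4.3 offers it without an arm limit; its timing relative to clinic randomisation is open, and no analysis uses the REDCap flag

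*Combined protocol and SAP*

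**What the plan says.** Section 4.2 (Aims 2 and 3) has primary care clinicians review the EHR-derived list and remove patients for whom the intervention is unsuitable. Control clinics do this too, although they receive no mailing, "in order to have the most comparable groups". The next sentence concerns additions: "At intervention sites, clinicians will also be given the opportunity to suggest any additional patients at the clinic who meet the inclusion criteria". No matching offer to control clinics is stated. On additions the section then says: "Patients selected in this way will be noted in REDCap as having been selected through this alternate method".

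Section 4.3 describes a single email to the primary care clinicians of eligible patients, in which "clinicians will have one week to opt potential participants out, or to suggest an eligible patient we may have missed". It names no arm. The randomisation paragraph follows: "We will randomly select one clinic (or more, as needed to meet the target dyad sample size) within each system as the intervention clinic".

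The schedule in section 6.1 has a row "Allow clinician opt-out of participants" directly above a row "Clinic randomization". Both are marked in Month 5-6.

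Under section 6.2.2, a patient found eligible on chart review and mailed the tool is enrolled. Section 1.2 defines feasibility as a proportion of enrollees. Section 9.5 applies the four-month TSDD query to all participants. Sections 9.1 to 9.5 do not mention the REDCap flag.

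**The concern.** Allocation is by clinic, so the arms are comparable only if patients are found by the same process on both sides. Symmetric opt-out protects this, and an addition route in one arm undoes part of it. The study team can restrict the offer to intervention sites only if it already knows which sites those are. The documents do not say whether clinicians know their arm when they reply. Patients named by a clinician after allocation may differ from those found by the search.

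Two outputs are exposed. One is the TSDD summaries by group: the variability of change and the within-clinic correlation that section 9.5 says the pilot will supply. The other is the proportion with a documented discussion among the 60 intervention patients. Its lower confidence limit is set against a 50% target in section 9.2, and meeting that target opens the way to the full ePCT. The nominating clinicians are primary care clinicians, and their notes are among those reviewed for that outcome (section 6.2.3).

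**Working it through.** **1. Texts compared.**
- Who may add: 4.2 words the offer for intervention sites; 4.3 has no arm limit. Both cannot be followed as written.
- When: 4.2 presupposes allocation. Paragraph order in 4.3 and row order in 6.1 suggest opt-out first, but neither states a before or after, and both 6.1 rows share one two-month column. The order is open.
- How analysed: added patients are flagged, enrolled and counted, with no separate report.

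**2. The plan's own figures.** Section 9.2 gives lower 95% limits of 51.6% and 62.1% for n=60 at 65% and 75%. The exact (Clopper-Pearson) limit, the 0.025 quantile of Beta(x, n−x+1), gives 51.6% for 39/60 and 62.1% for 45/60, so both reproduce. For 38/60 it is 49.9%, so meeting the target needs at least 39 of 60.

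**3. Feasibility proportion, additions replacing others within the 60.** The number added, k, and their difference in discussion rate, d, are assumptions; the documents give neither. P(X ≥ 39) with X = Bin(60−k, p) + Bin(k, p+d), by exact convolution:

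| p | k=0 | k=3, d=−0.20 / +0.20 | k=6 | k=12 |
|---|---|---|---|---|
| 0.65 | 56% | 49% / 62% | 43% / 69% | 31% / 80% |
| 0.70 | 84% | – | 74% / 91% | – |
| 0.75 | 97% | – | 94% / 99% | – |

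For scale, k=6 with d=0.20 moves the expected count by 6 × 0.20 = 1.2 patients. The sampling SD of the count is √(60 × 0.65 × 0.35) = 3.7.

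**4. Additions on top of the 60.** With six added, n=66. The exact limit is 49.3% for 41/66 and 50.9% for 42/66, so the threshold is 42. For X = Bin(60, 0.65) + Bin(6, 0.65+d), P(X ≥ 42) is 65% at d=0, 52% at d=−0.20 and 76% at d=+0.20. The levels differ from step 3 because n and the threshold change. The movement from no difference is similar: down 13 or up 13 points in step 3 (56% to 43% or 69%), and down 13 or up 11 here.

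**5. TSDD, with k=6 of 60 and an assumed difference δ of 0.25 to 1.0 SD.**
- Mean change in the intervention group shifts by (6/60) × δ = 0.025 to 0.10 SD.
- The SE of a difference between two groups of 60 is √((2/60)(1 + 29 × ICC)) SD, with 30 per clinic: 0.18 at ICC 0, 0.21 at 0.01 and 0.29 at 0.05 (ICCs assumed).
- The SD of change, one of the stated deliverables, is multiplied by √(1 + 0.1 × 0.9 × δ²) = 1.003 to 1.044, a rise of 0.3% to 4.4%. The relative sampling error of an SD from 60 patients is about 1/√(2 × 59) = 9% (normality, no clustering).
- No effect on the within-clinic correlation was calculated.

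**6. What symmetry changes.** The feasibility proportion uses intervention patients only. If suggestion is offered in both arms, added intervention patients can still be among those counted, and steps 3 and 4 stand. Symmetry restores comparable assembly of the arms; it does not by itself protect this proportion.

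**The case against.** The strongest reply is that little harm is shown. The pilot is stated not to be designed or powered for a significant change and plans no between-arm test. Suggested patients must meet the inclusion criteria and pass chart review, so they belong to the target population and were merely missed by the search. Clinics are paired on panel characteristics, opt-out is symmetric, and the flag permits separate reporting. All of this stands, and it limits the size of the problem. It does not settle which of two differing rules applies, or when the list closes relative to allocation.

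A reader might go further in four ways that the documents do not support:
- **That the plan fixes opt-out before randomisation, so 4.2 breaks a dated sequence.** Only paragraph and row order point that way, within one Month 5-6 column.
- **That control clinicians are expressly barred from suggesting patients.** This is inferred from the wording for intervention sites. A later sentence in 4.2 about doctors who wish to suggest patients names no arm, nor does 4.3.
- **That the route will bias the decision to proceed.** Every probability in the working beyond the no-addition figures rests on an assumed k and d and on whether additions replace or extend the 60.
- **That added patients escape the requirement of an "ambulatory care encounter with a primary care clinician (internal medicine, family medicine, or geriatrics) during the preceding 12 months".** It is absent from the 4.1 criteria, but 4.3 speaks of an eligible patient, which can be read to include it.

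**Conclusion.** The point holds as a rule to reconcile and a reporting gap. Sections 4.2 and 4.3 differ on who may add patients, the order relative to allocation is unresolved, and following 4.2 as worded allows post-allocation entry in one arm. Section 9 has no provision for the patients concerned.

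The size and direction of any effect are unknown from the documents. Under the assumptions shown, the TSDD effect is probably small against sampling error. The feasibility proportion is more sensitive when the true rate is near 65%, the lower planning value, where six additions differing by 20 points move the chance of meeting the target by 11 to 13 points. Near 75% there is little consequence: 97% becomes 94% or 99%. This should be fixed because the repair is cheap, not because a material bias has been demonstrated. Confidence is high on the difference in wording and lower on its consequences.

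**What to change.** Reconcile 4.2, 4.3 and 6.1 to one stated order: EHR list; opt-out and suggestion on the same terms at all clinics (or suggestion at none); list closed; allocation then made or disclosed; mailing. Apply the same order to any clinics added later to reach 120.

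Because symmetric suggestion alone leaves the feasibility proportion exposed, add to 9.5: counts by entry route and arm; all enrollees kept in the main analysis; and the feasibility proportion and TSDD summaries repeated without flagged patients.

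The cost is mostly wording and the order of steps already placed in Month 5-6. Suggestion in both arms adds minor eligibility review, REDCap entry and outcome extraction for suggested control patients. Dropping suggestion avoids that work but loses a few patients missed by the search, which could make the 60 harder to fill. The main analysis loses no precision. In the sensitivity analysis only, the exact lower limit at an observed 65% falls from 51.6% (n=60) to 51.2% (n=57), 50.8% (n=54) or 49.9% (n=48), using fractional counts where 65% of n is not whole. The change in order must come before randomisation; after that, only the reporting can be repaired.
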